
Date

Operating room or cluster scheduled

Printed name of requesting anesthesia personnel

- 2. A kit of controlled substances will be dispensed to the anesthesia personnel. The kit will be labeled with the anesthesia personnel's name, the drug content of the kit, and the issue number of the Controlled Substance Administration Record.
- 3. The drug kit must remain with the anesthesia providercand cannot be left unattended at any time.
- 4. The anesthesia personnel signs for drugs on the Controlled Substance Administration Record.
- 5. The Controlled Substance Administration Record will be retained by the anesthesia personnel for documentation of the day's cases.
- 6. No preexisting drug kit will be supplemented with additional drugs without the pharmacy slip issued with the original drug kit. If an attending wishes to supplement a resident's drug pack, they may do so only if they present the pharmacy drug slip to the pharmacist.

II. Documentation

- A. Controlled Substance Administration Record
 - 1) For each case, the anesthesia personnel will fill in the required information on the Controlled Substance Admin istration Record, including:

Patient name

	Protocol Name:	Ketamine and Propofol Combination versus Propofol for Upper
		Gastrointestinal Endoscopy
	Principal Investigator:	[name]
	Primary Contact	[name]
	Name/Contact Info:	[contact]; [contact]
	Date Revised:	08/28/2015
	Study Number:	IF#: 1790780

Number of ampules/tubexes of each drug administered Signature of the administering anesthesia personnel

- 2) Full doses not administered must be returned to the Pharmacy. Partial doses remaining after parenteral administrationmay not be discarded, but must be returned.
- 3) In the event an ampule/tubex is broken, the record of breakage should be noted on the Controlled Substance Administration Record and co-signed by a witnessing physician, R.N. or pharmacist.
- 4) Each ampule or vial of a controlled substance can only be used for an individual patient, and the waste returned (see "return of Drugs" below)

III. Return of Drugs

A. OR

- 1. The anesthesia personnel must return all unused drugs to the pharmacy before 7:00 PM along with the Controlled Substance Administration Record.
- 2. The anesthesia personnel reconciles any discrepancies and signs daily dispersing log. Amt. Returned = Amt. Issued -c(Amt. Administered + Amt. Wasted + Amt. Broken)
- 3. All drugs including unused propofol, etomidate, remifentanil and ketamine, must be accounted for, documented and returned to the pharmacy with the proper patient information.
- 4. Narcotic bags obtained from discontinued PCA's or epidural infusions must be accounted for, documented and returned to the pharmacy with the proper patient information.
- 5. No drawn up drug is to be wasted, i.e., squirted out, and must be accounted for, documented and returned to the pharmacy, including unused propofol, etomidate, ketamine, thiopental, fentanyl, midazolam etc.
- 6. No one is to exchange an intact vial of medication for a drug previously drawn up I nto a syringe.
- 7. When the anesthesia care team is relieved by another team, any unused, controlled medications in syringes, must be returned to the pharmacy by the original anesthesia care giver and must not be turned over to the new anesthesia care team to be given later in the case.

Protocol Name:	Ketamine and Propofol Combination versus Propofol for Upper Gastrointestinal Endoscopy
Principal Investigator:	[name]
Primary Contact	[name]
Name/Contact Info:	[contact]; [contact]
Date Revised:	08/28/2015
Study Number:	IF#: 1790780

- 8. Anesthesia personnel on-call and those whose cases extend beyond 7:00 PM return unused drugs and the Controlled Substance Administration Record to a locked repository box outside the pharmacy.
- 9. Any discrepancy is reconciled by the anesthesia personnel the following morning

Ketamine and Propofol Combination Versus Propofol for Upper Gastrointestinal Endoscopy
Data Analysis Plan

PI: [name]

NCT02643979

Document Date: 12/20/2015

Ketamine and Propofol Combination Versus Propofol for Upper Gastrointestinal Endoscopy
NCT02643979
12/20/2015

Statistical Plan and Analysis:

All variables will be checked for normality via Shapiro Wilk Test. Our primary endpoint, since it is categorical in nature will be analyzed via chi square test. Each other categorical variable will be analyzed via chi square testing as well. For normally distributed variables, t-test will be used. For non-normally distributed variables non parametric tests such as Mann-Whitney-U and Wilcoxon Rank Sum will be used. Significance testing will all be two tailed, with a cutoff of 0.05 as the threshold for statistical significance.

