Literature was reviewed regarding the use of ketamine for procedural sedation in the bronchoscopy and endoscopy suite as well as sedation for emergency department procedures. The combination of ketamine with other anesthetic agents has been shown to result in decreased dosage requirements of other agents, decreased incidence of airway obstruction requiring assistance, and mixed results regarding recovery time with some studies demonstrating quicker recovery including in obese patients and others demonstrating unchanged or prolonged recovery times with higher doses (2mg/kg) of ketamine. A large portion of the literature focuses on the use of ketamine in procedural sedation for emergency department (ED) procedures, especially in the pediatric population. Studies involving adults and endoscopy/bronchoscopy demonstrate overall positive results, however there is a dearth of literature involving the use of ketamine in the obese population.

The benefits of ketamine compared to most other anesthetic agents lie in its ability to produce hypnosis and analgesia with minimal respiratory depression and in some cases stimulatory effects on respiratory drive. The population that would stand to benefit most from these attributes of the medication are those prone to airway obstruction such as overweight individuals. This is especially salient given the fact that individuals with a higher BMI may require higher doses of propofol, which causes significant respiratory depression and increased incidences of airway obstruction.

As more patients turn to bariatric surgery as a method of weight loss when conservative measures fail, there is an increased need for upper endoscopies on this population prior to the surgery. High BMI patients present a unique challenge to the anesthesiologist due to an unfortunate coupling of increased medication dosage and a higher risk of airway obstruction and desaturation due to changes in body habitus. As mentioned previously, the benefits of ketamine could significantly benefit this population due not only to the attributes of this medication but its ability to decrease the overall propofol dosage required to tolerate upper endoscopy.

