The four clinicians involved in patient selection, protocol creation, and carrying out the study are all in constant communication throughout the process. The endoscopy center performs these procedures on a daily basis, many of whom would be candidates for our study. We aim to recruit 100 patients, and predict we can reach this goal within 6 months based on prior schedules.

5) Study Design

a) Recruitment Methods

Primarily recruitment of subjects will be through [name] practice involving patients receive an upper endoscopy prior to bariatric surgery.

Recruitment materials will primarily consist of a verbal explanation of the procedure to be performed, how it is normally carried out from the anesthetic perspective, and our primarily goal of adding ketamine to the induction agent.

b) Inclusion and Exclusion Criteria

Eligible patient population will consist of [name] patient population who are undergoing an upper GI endoscopy prior to consideration for bariatric surgery.

Protocol Name:	Ketamine and Propofol Combination versus Propofol for Upper
	Gastrointestinal Endoscopy
Principal Investigator:	[name]
Primary Contact	[name]
Name/Contact Info:	[contact]; [contact]
Date Revised:	08/28/2015
Study Number:	IF#: 1790780

Exclusion criteria consist of: History of schizophrenia/schizoaffective disorder/bipolar disorder/dementia, glaucoma, craniofacial abnormalities, epilepsy, allergy to study drugs (propofol or ketamine), or history of current intracranial mass lesion.

c) Number of Subjects

A preliminary power analysis predicted we need 30 patients per group (total 90) to have significance using a Wilcox Rank Sum Test assuming skewed data. We therefore intend to enroll 100 patients to account or potential subjects who may not be appropriate for inclusion in statistical analysis after data collection.

d) Study Timelines

Each individual subject will be followed until discharge from the PACU when the patient has made both the clinical endpoints as well as standard discharge criteria. We anticipate to enroll all patients within one year. We estimate that the study will be completed six months after the enrollment of all subjects.

e) Endpoints

Primary endpoint is the incidence of gagging on endoscope insertion.

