Secondary endpoints consist of: mean arterial pressure and heart rate during procedure, dosage required to achieve conditions necessary to proceed with upper endoscopy, total dosage of medication used, incidence of peri-procedure or post-operative nausea and vomiting, incidence of airway obstruction necessitating airway maneuvering (chin lift, jaw thrust, etc.), incidence of emergence delirium, and time required until eligible for discharge from endoscopy post-anesthesia care unit (PACU).

Since repeat ketamine doses will not be administered there are no specific primary or secondary endpoint parameters that would result in an end of study. In the event that unsafe vital signs changes or reaction to endoscopy occurred, the procedure would be aborted as would be standard protocol at our institution.

f) Procedures Involved in the Human Research

The study design is a prospective clinical study regarding the use of a 1:2 Ketamine: Propofol mixture (50mg Ketamine to 100mg Propofol) for induction in the study arm compared to a sole 100mg Propofol induction technique. Following this all follow up boluses will consist of only propofol in both arms. Subjects will be evaluated for response to initial insertion of endoscope, need for follow up doses, changes in vital signs, incidence of airway obstruction, incidence of emergence delirium, and time to discharge from the PACU. No further follow up or evaluation is planned.

Protocol Name:	Ketamine and Propofol Combination versus Propofol for Upper
	Gastrointestinal Endoscopy
Principal Investigator:	[name]
Primary Contact	[name]
Name/Contact Info:	[contact]; [contact]
Date Revised:	08/28/2015
Study Number:	IF#: 1790780

The primary study protocol procedure is the administration of a ketamine vs. propofol and ketamine mixture with induction of anesthesia. The remainder of monitoring for safety and risk management are part of the normal anesthetic care all patients receiving upper endoscopy and evaluation prior to PACU discharge receive. Standard anesthetic monitors and vital sign monitoring will only differ in study patients in the use of a pre-determined 3-minute non-invasive blood pressure monitoring interval instead of the minimum 5-minute interval advised by the ASA.

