Exclusion criteria is almost entirely based on comorbidities and conditions that have an association with an untoward reaction or intolerance to ketamine. In addition, the blood pressure monitoring intervals of 3 minutes are more frequent than the standard recommendation of 5 minutes, which allows providers to be more aware of any blood pressure changes as a result of the ketamine administration. In addition, upper endoscopy will not proceed until patient demonstrates an adequate Ramsay sedation scale score of >5 to reduce incidence of patient discomfort or recall.

Source records will include the patients chart for the specific endoscopy encounter in epic which will be used for demographic information and to monitor the patient's length of stay and any events that occurred in the endoscopy PACU. Compurecord will be used to collect data regarding medication administration, vital signs, and any intraoperative events including toleration of upper endoscopy and incidence of airway obstruction.

No data will be collected in the form of long-term follow up.

g) Specimen Banking

N/A

h) Data Management and Confidentiality

Data will be collected on paper that will indicate the patient's medical record and her study number assignment, and her initials. There will be no indication on these sheets of the patient's name. The data collection sheet is attached. The data on the sheets will be transferred to an Excel computerized spreadsheet without the patient's initials. The excel data base is in a computer with a password. Also, the excel program is protected by a password. Data will also be encrypted for confidentiality. We will have a separate binder that will have the patients name along with their medical record # should we need to recheck records for any reason. The binder with the data sheet will be kept in the co-investigator's office near the endoscopy suite that is kept locked at all times and can only be accessed through T-9 door code. The binder with the identifying information will be kept in the principal investigator's office, also a locked office via T9 code that is in a different building. Only the PI will have access to these records.

i) Provisions to Monitor the Data to Ensure the Safety of Subjects

There is no anticipation of more than minimal risk involved to subjects.

Mount Sinai

Protocol Name:	Ketamine and Propofol Combination versus Propofol for Upper
	Gastrointestinal Endoscopy
Principal Investigator:	[name]
Primary Contact	[name]

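### The secondary propofol-dose endpoints are compared without adjustment for BMI, which the protocol names as a possible driver of dose; the cost is precision, not validity

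*SAP*

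**What the plan says.** The SAP's only analysis section, Statistical Plan and Analysis, is one paragraph. After a Shapiro-Wilk check it splits continuous variables two ways: "For normally distributed variables, t-test will be used", and "For non-normally distributed variables non parametric tests such as Mann-Whitney-U and Wilcoxon Rank Sum will be used". On error rates it says: "Significance testing will all be two tailed, with a cutoff of 0.05 as the threshold for statistical significance". It mentions no covariate, stratification factor or regression model.

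Protocol section 5e (Endpoints) lists among the secondary endpoints "dosage required to achieve conditions necessary to proceed with upper endoscopy, total dosage of medication used". Both fall under the tests above. The primary endpoint is a different kind of variable: "Primary endpoint is the incidence of gagging on endoscope insertion".

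Protocol section 2 (Background) says that "individuals with a higher BMI may require higher doses of propofol". Under section 5f (Procedures), both arms receive the same 100 mg propofol component at induction, and any later boluses are propofol alone. The same section names the endoscopy chart as a source record, "which will be used for demographic information", without listing the variables. Section 9 refers to the information gathered in a standard anesthesia pre-operative assessment.

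**The concern.** Because the propofol component of induction is a fixed amount, any extra need linked to body size has to appear in the boluses that follow, and so in the dose endpoints. The protocol itself raises BMI as a possible source of that need. When a baseline variable predicts the outcome, leaving it out of the model leaves its share of the variation in the error term, and the interval for the treatment difference is wider than it has to be.

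The dose endpoints bear on one of the reasons the background gives for adding ketamine, namely that less propofol would be needed. A less precise comparison makes a real saving harder to show. The stake is limited to these two secondary endpoints.

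**Working it through.** **The plan's own figure.** Protocol section 5c gives 30 patients per group, 90 in total, for a Wilcoxon rank-sum test, with 100 to be enrolled. It states no endpoint, effect size, SD or power, so the calculation cannot be reproduced. Its arithmetic does not fit two arms either: 2 × 30 = 60, whereas 90 / 2 = 45. That discrepancy needs reconciling separately and does not drive this point. For scale, the standardised difference detectable with 80% power at two-sided 0.05 is (1.960 + 0.842) × √(2/n), divided by √(3/π) for the Wilcoxon test under normality:

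| n per arm | t-test | Wilcoxon |
|---|---|---|
| 30 | 0.72 SD | 0.74 SD |
| 45 | 0.59 SD | 0.60 SD |
| 50 | 0.56 SD | 0.57 SD |

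**Inputs for the adjustment.** The two-sided 0.05 level comes from the SAP. The correlation r between baseline BMI and (log) dose is an assumption, taken from 0.1 to 0.6; the protocol reports having no pilot data. The reference case is an effect that the unadjusted comparison would detect with 80% power.

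**Formulas.**
- Residual SD after adjustment = SD × √(1 − r²), so the standard error falls by 1 − √(1 − r²).
- Equivalent saving in sample size = r².
- Power after adjustment = Φ(2.802 / √(1 − r²) − 1.960).

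At r = 0.3, for example, √(1 − 0.09) = 0.954 and 2.802 / 0.954 − 1.960 = 0.977, so power is Φ(0.977) = 83.6%.

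| Assumed r | SE reduction | Sample-size equivalent | Power (from 80%) |
|---|---|---|---|
| 0.1 | 0.5% | 1% | 80.4% |
| 0.2 | 2.0% | 4% | 81.6% |
| 0.3 | 4.6% | 9% | 83.6% |
| 0.4 | 8.3% | 16% | 86.4% |
| 0.5 | 13.4% | 25% | 89.9% |
| 0.6 | 20.0% | 36% | 93.8% |

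**Small-sample check.** A noncentral-t calculation with 45 per arm, giving up one degree of freedom for the covariate, yields 79.1% unadjusted, 79.5% at r = 0.1, 82.7% at r = 0.3 and 89.2% at r = 0.5. The pattern is the same, and the lost degree of freedom costs almost nothing.

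**Limit of the calculation.** It compares adjusted with unadjusted means on a scale where the errors are roughly normal. If doses are skewed, the SAP would use a rank test, and the gain over that test was not computed. The table is therefore approximate.

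**The case against.** The strongest reply is that this is a preference and not an error. A t-test or rank-sum test is a valid comparison of randomised arms, and its error rate already allows for chance imbalance in BMI. That stands. A reader might infer that omitting BMI biases the dose comparison, but the documents do not support this. They do not describe how patients are assigned. If assignment is random, there is no bias; if it is not, BMI imbalance could bias the comparison, but that would be a problem of allocation and a separate question.

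A reader might also take the protocol to say that dose rises steadily with BMI in this sample. It says only that higher-BMI individuals may need more. All participants are bariatric candidates, so the BMI range may be narrow and r small, although section 5b sets no BMI limits. A material loss of precision is therefore possible but not shown.

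Three further points stand:
- The documents give no unit for dose. An analysis per kilogram would already deal with part of the body-size effect.
- BMI, height and weight are not named as collected variables, and the data sheet is not shown. Their availability is an inference.
- Patients who need no extra propofol before insertion would all have the same value for that endpoint. A log-linear model fits such a cluster poorly.

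These points reduce the claim and shape the fix. They do not remove the case for adjusting total propofol dose, where a weak covariate costs about one degree of freedom and a useful one brings a real gain.

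**Conclusion.** The point holds as a minor matter of efficiency. The SAP plans unadjusted tests for two secondary dose endpoints, while the protocol itself names a plausible baseline predictor. The gain from adjustment is negligible below about r = 0.2 and becomes material from about r = 0.4; where this trial lies in that range cannot be learned from the documents. The conclusion assumes random allocation, a BMI or weight value recorded at baseline, and approximate normality of log dose. Nothing here affects the primary endpoint or makes the planned tests invalid.

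**What to change.** Add a short paragraph to the SAP before any data are examined by arm; choosing the covariate after seeing results would invite selective reporting.

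- **Total propofol dose.** Fit a linear model of log dose in mg on arm plus baseline BMI (or weight, with the choice named in advance). Report the ratio of geometric means with a 95% CI. Keep the planned Wilcoxon test as a sensitivity analysis. State that the variable is propofol alone, since the endpoint as worded, "total dosage of medication used", does not say so.
- **Dose to reach insertion conditions.** Use a proportional-odds model with arm and baseline BMI, because values may cluster at the fixed induction amount.
- **Data.** Confirm that height and weight from the standard pre-operative assessment are on the data collection sheet, and add them if they are not.

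The cost is a few lines of SAP text and possibly two fields on the data sheet. Dosing and conduct do not change. The downside is a model assumption on secondary endpoints only; for total dose, the retained rank test shows whether the conclusion depends on it.
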